## **Decision-making in NoLAP Patients**

For each NoLAP patient, the local team will be asked to select from 5 options who or what specialty was involved in making the decision: patient, surgical, anaesthetic, intensive care or other speciality. If more than one option is selected, the local team will be asked to specify the main two. Next, a list of potential influencing factors will be selected by the local team to improve our understanding of the decision-making process [Appendix]. A patient's decision is defined as either by the patient themselves or next of kin (as determined by clinical team) or patient's wishes already known and documented e.g. living will). Highest level of clinical seniority involved in the decision-making can be in person or by telephone. Free text will be added to allow further reasoning.

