## Aims

This study aims to:

1) Identify a U.K. consecutive series of older adults presenting with acute abdominal pathology potentially treatable by emergency laparotomy where the decision is made not to undergo surgery (NoLAP) and their associated 90-day mortality.

2) Collect, define and characterise the reasoning behind the NOLAP decision.

3) Define potential prognostic markers for mortality that could aid decision-making in the future (including frailty, NELA score and sarcopenia).

4) Compare aims 1 and 3 to those that underwent surgery (ELAP) during the same time frame as the NoLAP population.

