# Appendix A. Decision-making Options for NoLAP.

Must select at least one of these factors as the MAIN influencing factor.

Patient Factors	Yes/	Surgical Factors	Yes/
	No		No
Patient does not wish to have surgery (Drop down menu of reasons if selecting 'yes': chronic pain, management of stoma, does not want to lose independence i.e. institutionalisation, other – free text)		Poor Pre-op Fitness (Drop-down menu options if selecting 'yes': home oxygen; nursing home resident; bed bound; housebound; advanced comorbidity; other – free text)	
Has Living will in place		Poor prognostic pathology (Drop-down menu options if selecting 'yes': global ischaemia, advanced malignancy; other –free text)	
Patient involved in decision (Drop-down options if selecting 'no': Reduced GCS; severe dementia; acute delirium; power of attorney in place; other – free text)		
 
High prognostic score
 
(Drop-down menu options if selecting 'yes': high NELA score; high frailty score; high P-Possum score, high SORT score)
 
If frailty score used: define which score
 
If yes selected for any score, record actual value (frailty score value or predicted mortality value)
 
	
Anyone else representing the patient involved in the decision (Drop down options if selecting 'yes': next of kin, legal guardian, friend, other)		Surgeon involved in decision (Drop-down menu if selecting 'yes': consultant, associate specialist, staff grade, registrar, core trainee)	

Anaesthetic Factors	Yes/	Intensive Care Factors	Yes/
	No		No
Poor Pre-op Fitness		Poor Pre-op Fitness	
(Drop-down menu options: home oxygen; nursing home resident; bed bound; housebound; advanced comorbidity; other – free text)		(Drop-down menu options: home oxygen; nursing home resident; bed bound; housebound; advanced comorbidity; other – free text)	
Poor prognostic pathology		Poor prognostic pathology	
(Drop-down menu options: global		(Drop-down menu options: global ischaemia,	

ischaemia, advanced malignancy; other –		advanced malignancy; other -free text)	
free text)			
,			
High prognostic score		High prognostic score	
(Drop down many options if colocting was'		(Drop down many options if colocting (yes), high	
(Drop-down menu options if selecting 'yes':		(Drop-down menu options if selecting 'yes': high	
high NELA score; high frailty score; high P-		NELA score; high P-Possum score; high SORT score;	
Possum score; high SORT score)		high frailty score)	

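### The decision-source item counts next-of-kin decisions as 'patient', has no code for a guardian or attorney, and can be only partly untangled from Appendix A

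*Protocol*

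**What the plan says.** The second aim in the protocol's Aims section is to "Collect, define and characterise the reasoning behind the NOLAP decision". The same subject is the secondary objective in the Study Synopsis, the first secondary outcome under Outcomes, and Paper 3 under Study Dissemination.

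The data for it come from two places.

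- **Decision-source item** (Decision-making in NoLAP Patients). The local team is to "select from 5 options who or what specialty was involved in making the decision: patient, surgical, anaesthetic, intensive care or other speciality". Several may be chosen: "If more than one option is selected, the local team will be asked to specify the main two". A patient's "decision is defined as either by the patient themselves or next of kin (as determined by clinical team"). The same code also covers wishes that the patient had put on record beforehand, with a living will as the example. Three sources of authority therefore share one code.
- **Factor list** (Appendix A). The same section says that "a list of potential influencing factors will be selected by the local team to improve our understanding of the decision-making process". Among the patient factors are separate yes/no items for the patient not wanting surgery, a living will, the patient's involvement in the decision, and "Anyone else representing the patient involved in the decision". If the patient was not involved, the reasons offered include "Reduced GCS; severe dementia; acute delirium; power of attorney in place". If a representative was involved, the choices are next of kin, legal guardian, friend or other.

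The proforma in Appendix B has no item on who made the decision.

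**The concern.** A site that follows the definition must record 'patient' when a relative declines surgery for someone who is unconscious or has severe dementia, because no other code fits. A table built from this item would show patient decisions, and a reader would naturally take them as choices made by patients.

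Whether the patient or someone speaking for the patient declined surgery is basic to an account of how these decisions are made. The Background section names limited information on the decision as a weakness of the earlier single-centre UK study, so this is a gap the study means to close. The pooling is also fixed at data capture. An analysis plan can cross-tabulate what was collected, but it cannot recover who decided if that was never asked.

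**Working it through.** The documents state no figure on this point, so none can be reproduced. The check sets the two instruments side by side for the kinds of case a site will meet.

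| Case | Decision-source item | Appendix A: patient involved | Appendix A: representative involved | Separable? |
|---|---|---|---|---|
| 1. Patient declines alone | patient | yes | no | yes |
| 2. Patient lacks capacity, relative decides | patient | no, with reason | yes, next of kin | yes |
| 3. Patient lacks capacity, living will applies, no relative involved | patient | no, with reason | no (living will: yes) | yes |
| 4. Patient and relative both take part | patient | yes | yes, next of kin | no |
| 5. Guardian or attorney decides | no rule given | no, with reason | yes, guardian or other | in Appendix A only; source code may vary by site |

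Four things follow.

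1. In cases 1 to 3 the source item gives one code for three different situations, but Appendix A tells them apart.
2. In case 4 Appendix A shows that both were involved, not whose decision it was. The ranking of the main two sources cannot settle this, because patient and relative are the same option. If they were the two main decision-makers, the ranking shows one category.
3. In case 5 the two lists do not match. The source item names only next of kin. Appendix A adds legal guardian, friend and other, and lists power of attorney as a reason for non-involvement. Sites have no instruction on which source code to use.
4. The protocol does not say whether the Appendix A item on the patient not wanting surgery may be ticked on a relative's word. If sites carry the broad definition across, an item that could help to check the pooling is affected by it too.

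**Illustration of size (all inputs assumed).** Let P be the share of NoLAP decisions coded 'patient', and q the share of those made by next of kin alone. The share made by the patient, in person or through documented wishes, is P × (1 − q). The excess, if the item is read as the patient's own choice, is P × q. Take P = 40%:

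- q = 10%: 40% × 0.90 = 36%, excess 4 points
- q = 25%: 40% × 0.75 = 30%, excess 10 points
- q = 40%: 40% × 0.60 = 24%, excess 16 points
- q = 50%: 40% × 0.50 = 20%, excess 20 points

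Neither P nor q is in the documents. The spread shows only that the excess depends wholly on an unknown share.

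**The case against.** The best defence is that the protocol already collects what is needed. Appendix A holds separate items on patient involvement, reasons for non-involvement, representatives and living wills. It also requires at least one factor to be named as the main one, and free text is allowed. A next-of-kin decision for a patient who was not involved can be found in the data as designed. This stands, and it removes most of the force from any claim of unavoidable bias.

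A reader might infer that aim 2 *will* overstate patients' own choice. The documents do not support that. No section says that the pooled item will be reported alone or presented as the patient's own choice, and no stated outcome is the proportion of patients who themselves declined. The source item also asks who was involved and allows several answers, so it is not an exclusive record of who decided.

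A reader might also see a contradiction when a record shows 'patient' as a source and the patient as not involved. Under the protocol's own broad definition that record is consistent, and it is the combination that marks a decision by proxy or by documented wishes.

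It can further be said that tabulation belongs in the SAP, which the Data analysis section promises and which is not at hand. That holds for cross-classification. It does not hold for the response options and the definition, which the protocol fixes. What remains is that joint cases cannot be cleanly attributed and that guardians and attorneys have no source code. Naming a main factor may help in some joint cases, but nothing says that the main factor identifies who decided.

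**Conclusion.** The point holds as a defect in how one item is defined and labelled. The decision-source item pools the patient's own decision, next-of-kin decisions and documented wishes, and gives no code for a guardian or attorney. It *can* overstate how often patients themselves declined surgery, on condition that it is reported as the patient's own choice without the Appendix A items. The size is unknown: the 4 to 20 points above rest on assumed inputs and are not an estimate for this study. Cases where the patient was not involved and a representative was can be separated. Cases where both took part cannot. This affects a secondary aim only and leaves the primary outcome and the sample size untouched. It is worth correcting because the correction is cheap.

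**What to change.** **Before data entry.** In Decision-making in NoLAP Patients, limit 'patient' to the patient in person or the patient's own documented wishes. Add a sixth source, 'representative (next of kin, guardian, attorney)', and let it be ranked among the main two. Report the two sources separately. When a relative and the patient both took part, the ranking can then show whether each was a main source.

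**If data are already collected.** Report the 'patient' category cross-classified with the two Appendix A items on patient involvement and on involvement of a representative. Show the group in which both took part as its own row rather than assigning it to either side.

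**Cost.** One definition, one extra REDCap option and slightly smaller categories. Appendix A already asks sites about both kinds of involvement, so the added burden is close to nil.

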#### Sarcopenia Measurement: CT Scan Analysis

To measure sarcopenia on each patient, the total cross-sectional area of the psoas muscles (Total Psoas Area, TPA) will be measured using one of the following techniques: a manual technique or a semi-automated CT planimetry using validated software (ImageJ). Each site will have the option of undergoing a teaching package to train them in muscle mass measurement. Or, alternatively the PAC images can be sent centrally to the study team to analyse.

For the manual technique, psoas muscle will be measured at the level of the L3 vertebra on pre-operative CT (must be within 3 days of laparotomy decision). To ensure standardisation, the exact level of measurement is defined as the CT slice in which both transverse processes were maximally in view. Area will be measured using a free-hand drawing technique on Picture Archiving and Communication System (PACS) software. The outline of each individual psoas muscle will be traced, the area calculated, and summated to provide the TPA (mm^2). The TPA will then be standardised for patient height using the formula TPA (mm^2) / height (m^2) to provide the total psoas index (TPI) for each patient.

For the purposes of this study the threshold values used for the diagnosis of sarcopenia are the same as those used by Prado et al in their widely cited 2008 paper [9]. This entails a figure of 524 mm^2/m^2 for males, and 385 mm^2/m^2 for females. All individuals with a TPI below this threshold for their gender were classified as sarcopenic. Intra- and Interclass correlation coefficients will be performed on twenty randomly selected CT scans for 2 blinded analysers to measure sarcopenia. ICCC is expected to be at least 0.75 for both sets of scores.

For the semi-automated technique, whole-slice analysis at the L3 level will be measured using semi-automated CT planimetry through the validated software package ImageJ (ImageJ) [10-15]. DICOM images from Picture Archiving and Communication System (PACS) will allow for the measurement of tissue radio-density, including muscle and adipose tissue will be taken, while conversion calculations will be performed to allow for the analysis of all types of CT scan (plain/arterial/portal venous). Calculated values will be stratified by BMI and

compared to validated threshold values used for the diagnosis of sarcopenia Clinical frailty scores will be used as an objective measure of sarcopenia in accordance with the European Working Group on Sarcopenia in Older People (EWGSOP statement) with comparisons made with CT-diagnosed sarcopenia through the calculation of correlation coefficients.

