#### **Profile of Centre**

Each site will be asked to complete a site profile questionnaire when they register. This will record the proposed site, NELA or ELLSA participation, number of ELAPs per month and names of team. In addition, each site will be asked for confirmation of their participation in the other arm of the study: sarcopenia. Each site will be asked for their radiological imaging system (e.g. PACS) and clarification of their local process of having the images transferred to the DtD Steering group to analyse.

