#### Variables collected

The following clinical parameters will be collected for NOLAP population: age; sex; place of residence (home with no carers, home with carers, intermediate care, residential home, nursing home); ASA (American Society of Anaesthesiologists); surgical diagnosis (pre-operatively); NELA score; Clinical Frailty Score (Rockwood, 1 to 7); co-morbidities (Charlson; total number of co-morbidities); polypharmacy (5+ medications: yes/no) CT performed within 48 hours of decision (yes/ no); CT

diagnosis; date of assessment for laparotomy, time of day and location (most relevant according to the following list: general surgical ward; other surgical ward; orthopaedics; gynaecology; geriatrics; acute medical ward; other medical ward). Preoperative (within 8 hours of surgical decision) blood markers will also be recorded: lactate; C reactive protein; creatinine and WCC. The actual procedure performed will be recorded for the ELAP patients only.

For comparison to ELAP. This data will be retrieved directly from NELA and ELLSA databases with no extra data required by each participating site.

Remaining variables: length of hospital stay; length of critical care stay (ICU and HDU combined). Both groups will then be followed up for: 30-day complications (Clavien-Dindo Grading); date of discharge; discharge destination (home with no carers, home with carers, intermediate care; residential home, nursing home); 30-day and 90-day mortality and death at 1 year. Actual date of death and cause of death (1a on death certificate) will be recorded.

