# Appendix B: Proforma

Q1	Study ID	
Q2	Age at admission to study (years)	
Q3	Sex	Male Female
Q4	Comorbidities	CCF Y/N COPD Y/N
		CVA Y/N Dementia Y/N
		Hemiplegia Y/N CKD Y/N
		Leukaemia Y/N DM(complicated) Y/N
		Lymphoma Y/N DM(uncomplicated)
		Y/N
		Mild liver disease Y/N IHD Y/N
		Severe liver disease Y/N PVD Y/N
		Solid tumour Y/N Metastatic tumour
		Y/N
		AIDS Y/N
		Other:
Q5	Polypharmacy (≥5 medications)	Yes No
Q6	Place of Surgical review (choose	Emergency Department
	most relevant)	General Surgical Ward
		Other Surgical ward
		Orthopaedics
		Geriatric ward
		Acute medical ward
		Other medical ward
Q7	Care level prior to admission	Home (no carers)
		Home (with carers)
		Residential Home
		Nursing home
		Intermediate care

		Other:
Q8	Frailty score	1,2,3,4,5,6,7
Q9	NELA score	%
Q10	Interval between admission and	
	laparotomy (days)	
Q11a	Pre-decision Creatinine	
Q11b	Pre-decision CRP	
Q11c	Pre-decision WCC	
Q11d	Pre-decision Lactate	
	(all within 8 hours of decision)	
Q11	Pre-operative clinical diagnosis	
Q12	CT performed pre-operatively	Yes/ no
	(within 24 hours of decision)	
Q13	CT diagnosis	
Q14	Psoas muscle mass (TPI)	
	[TPA/ height)	
Q15	ELAP?	Yes/ no
Q16	Day of decision	Monday to Thursday
		Friday to sunday
Q17	Time of decision (24 hour)	:
Q18	Operation performed at	
	laparotomy	
Q19	Length of stay post-operative or	
	NOLAP decision (days)	
Q20	Length of critical care stay (ICU and	
	HDU) (days)	
L	l	

Q21a	Post-operative complication within 30 days	Yes	No
Q21b	Grade of complication		
Q22	Care level on discharge	Home (no carers)	
		Home (with carers)	
		Residential Home	
		Nursing home	
		Intermediate care	
		Other:	
Q23	30 day mortality	Yes	No
Q24	30 day re-admission	Yes	No
Q25	90 day mortality	Yes	No
Q26	1 year mortality	Yes	No

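### Height, weight and raw psoas area have no data field, so the BMI strata and centrally read psoas index have no stated source, and the proforma's index formula omits the square

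*Protocol*

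**What the plan says.** Protocol, Aims, makes sarcopenia a candidate prognostic marker: "Define potential prognostic markers for mortality that could aid decision-making in the future (including frailty, NELA score and sarcopenia". Aim 4 extends that work to a comparison with patients who had the operation (ELAP).

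Protocol, Sarcopenia Measurement: CT Scan Analysis, gives two techniques.

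- **Manual.** Psoas area (TPA, mm²) is traced at L3 and indexed: "The TPA will then be standardised for patient height using the formula TPA", over height in m². The cut-offs are 524 mm²/m² for men and 385 mm²/m² for women: "All individuals with a TPI below this threshold for their gender were classified as sarcopenic".
- **Semi-automated.** For planimetry at the same level, the text says: "Calculated values will be stratified by BMI and" goes on to a comparison with published thresholds.

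Sites may measure the scans themselves, or "alternatively the PAC images can be sent centrally to the study team to analyse". Profile of Centre asks each site for "clarification of their local process of having the images transferred to the DtD Steering group to analyse". Both places speak of images only.

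Variables collected opens with "The following clinical parameters will be collected for NOLAP population: age; sex; place of residence" and continues through clinical scores, comorbidity, bloods and follow-up, with no height, weight or BMI. ELAP data are to come from the two national audits without further work by sites. In Appendix B the single sarcopenia item is Q14, "Psoas muscle mass (TPI"), annotated as TPA over height.

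**The concern.** A derived variable needs its inputs. TPI needs an area and a height, and BMI needs a height and a weight. If the form stores only the finished index, three things follow.

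1. The BMI grouping has nothing to draw on.
2. A central reader who receives images can measure an area but has no stated height to divide by.
3. An index calculated at a site cannot be recomputed from what is stored. This matters because the form and the methods section write the divisor differently.

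At stake is whether the sarcopenia marker in aims 3 and 4 is complete and means the same thing at every site. An analysis plan can choose how to handle a variable, but it cannot supply one that was not recorded.

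**Working it through.** The plan states no figure to reproduce here. The check sets required inputs against listed fields, then sizes the effect of the two divisors.

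**Step 1. Inputs against fields**

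| Input | Needed for | Variables collected | Proforma Q1–Q26 |
|---|---|---|---|
| Psoas area (mm²) | TPI | no | no (only the finished index, Q14) |
| Height | TPI, BMI | no | no |
| Weight | BMI | no | no |
| BMI | planimetry strata | no | no |
| Sex | sex-specific cut-off | yes | yes (Q3) |

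**Step 2. Can area be classified without height?**

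The area cut-off implied by a TPI threshold is: threshold × height². The thresholds are the protocol's. The heights are assumptions, since the document gives none.

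- Men: 524 × 1.60² = 1341 mm²; 524 × 1.75² = 1605 mm²; 524 × 1.90² = 1892 mm².
- Women: 385 × 1.45² = 809 mm²; 385 × 1.60² = 986 mm²; 385 × 1.75² = 1179 mm².

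From the shortest to the tallest, the cut-off rises by 1892/1341 − 1 = 41% in men and 1179/809 − 1 = 46% in women. Area alone therefore does not determine the classification.

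**Step 3. The two divisors**

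The methods section divides by m², and its thresholds carry the unit mm²/m². The Q14 annotation divides by height. An index calculated as annotated equals TPI × height, so at 1.75 m it is 1.75 times the intended value. Compared with the same thresholds, the implied area cut-off becomes threshold × height:

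- Man of 1.75 m: 524 × 1.75 = 917 mm², against 1605 mm².
- Woman of 1.60 m: 385 × 1.60 = 616 mm², against 986 mm².

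Example (assumed values): a man of 1.75 m with a psoas area of 1400 mm² has TPI 1400/1.75² = 457, below 524, so sarcopenic. Following the annotation gives 1400/1.75 = 800, so not sarcopenic. The error runs one way for anyone taller than 1 m: too few patients are called sarcopenic.

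**Step 4. Could it be repaired from the stored data?**

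Replacing TPA/height by TPA/height² needs height. With only the Q14 value stored, the correction cannot be made, and nothing on the form shows which divisor was used.

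**The case against.** **The lists are not exhaustive.** Variables collected names ASA grade and cause of death, which have no item in Q1–Q26. The proforma has TPI, which Variables collected omits. Absence from both is therefore not proof that height will never be obtained. Q14 itself presumes that whoever completes it has a height. A site could send height with the images, or finish Q14 once an area is returned. This stands. A reader might infer that TPI is impossible for every centrally read scan, but the document supports only that no source of height is stated.

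**Some checking is planned.** Validation covers 25% of fields in 10% of cases, and a reliability study uses twenty scans. So it would be too strong to say that site values cannot be checked at all. But validation is described as covering key demographic and outcome data without naming Q14, and 0.25 × 0.10 is 2.5% of field entries. Reader agreement on scans does not test the height or the divisor.

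**The annotation may be shorthand.** Q14 may be a loose label, or an exponent may have been lost in the text available here. Sites that follow the methods section would calculate the index as intended. This is fair: the divisor error is a risk created by two differing statements, not a predicted outcome.

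**Two further inferences are not supported.** One is a misclassification rate from inaccurate heights. That measures error in height, which recording height makes visible but does not remove, and it needs spreads and error sizes that the document does not give. The other is a selection effect through the reading route. That presumes that central reading yields no index and that the route chosen is related to outcome; the document shows neither.

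**Scope.** Sarcopenia is in neither the listed outcomes nor the adjusted mortality model (age, sex, frailty). This also stands.

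**Conclusion.** The point holds in a limited form. On the data the protocol lists, BMI stratification has no source, and TPI for centrally read scans has no stated source of height. The BMI gap is the firmest part, because no field presupposes BMI in the way that Q14 presupposes height. The proforma and the methods section also disagree on the divisor. A site that took the form literally would apply an area cut-off of 917 instead of 1605 mm² (man, 1.75 m) or 616 instead of 986 mm² (woman, 1.60 m), with no way to recompute from the stored data. Those areas rest on assumed heights; the missing inputs and the differing divisors do not.

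The consequence is confined to sarcopenia as a prognostic marker in aims 3 and 4. The primary outcome and the adjusted 90-day mortality comparison are untouched. The change should be made because it is cheap and the inputs are best captured prospectively, but the main result does not depend on it.

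**What to change.** - Add to Variables collected and Appendix B: height, weight, the source of each (measured, reported or estimated), and raw psoas area in mm².
- Derive TPI = TPA/height² and BMI = weight/height² centrally, for site-read and centrally read scans alike, instead of relying on a site-entered index.
- Correct the Q14 annotation so that it matches the methods section.
- State where height and weight come from for ELAP patients. The protocol promises no extra data entry by sites for them and names neither item among the audit data. If the audits do not hold them, either that promise or the aim 4 sarcopenia comparison has to change.

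The cost is about five REDCap items per patient (height, weight, two source items, area) and one derivation step. Some heights and weights will be estimates in acutely ill patients; the source items make that visible but do not cure it.

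### The two permitted sarcopenia techniques measure different quantities with no rule assigning them, and the proforma labels the index without squaring height and records neither height, BMI nor technique

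*Protocol*

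**What the plan says.** The Protocol section 'Sarcopenia Measurement: CT Scan Analysis' states that TPA "will be measured using one of the following techniques: a manual technique or a semi-automated CT planimetry using validated software (ImageJ".

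For the manual technique, each psoas is traced at L3, the two areas are summed to TPA in mm², and TPA is divided by height squared to give the TPI. Cut-offs of 524 mm²/m² for men and 385 mm²/m² for women follow, with the rule: "All individuals with a TPI below this threshold for their gender were classified as sarcopenic". The scan used "must be within 3 days of laparotomy decision".

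For the semi-automated technique, "whole-slice analysis at the L3 level will be measured using semi-automated CT planimetry". It covers the radio-density of muscle and fat. The results are to be split by BMI and compared with thresholds described as validated, but no values are given.

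On who measures, local reading after training is one route: "Each site will have the option of undergoing a teaching package to train them in muscle mass measurement". The other route is central reading by the study team, to whom a site may transfer its scans.

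In 'Appendix B: Proforma', Q14 is the only muscle field. It is labelled as psoas muscle mass (TPI), with a bracketed note giving TPA over height and no square. Q12 asks whether a CT was done "within 24 hours of decision". The corresponding item under 'Variables collected' reads "CT performed within 48 hours of decision".

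**The concern.** Aim 3 names sarcopenia as a candidate prognostic marker for mortality, and aim 4 carries the marker comparison over to patients who had surgery. Both need a value that means the same thing in every patient. The text puts that at risk in two ways.

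First, a patient read only by the whole-slice technique has no TPI, so the only classification rule with stated cut-offs cannot be applied. Second, if a value divided by height instead of height squared is compared with cut-offs in mm²/m², patients who are sarcopenic by the Methods definition are recorded as not sarcopenic. The form holds nothing that would reveal this. Either problem would misclassify the marker or make it non-comparable, and so distort its association with mortality.

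A smaller, separate matter is that one yes/no item about CT carries two different time windows.

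**Working it through.** The Protocol gives no figure on this point to reproduce. The check is a comparison of the texts, followed by arithmetic on the index.

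**1. What each technique delivers**

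| | Manual | Semi-automated |
|---|---|---|
| Structure measured | Both psoas muscles at L3 | Whole slice at L3, muscle and fat |
| Scaling | TPA / height² | Split by BMI |
| Cut-offs | 524 (men), 385 (women) mm²/m² | Not given |
| Field on the proforma | Q14 | None |
| Rule for who gets it | None | None |

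The opening sentence treats the two columns as routes to the same quantity, but the descriptions do not. The planned agreement check (twenty scans, two blinded analysers) concerns agreement between and within readers. No comparison of one technique with the other is stated.

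**2. What the form can hold**

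Raw TPA, height, BMI and technique appear neither under 'Variables collected' nor in the proforma. The BMI split therefore has no listed BMI to use, and a Q14 entry cannot be rescaled from the listed data.

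**3. Size of the index discrepancy**

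Inputs: the cut-offs 524 and 385 mm²/m² (Protocol, sarcopenia section) and height *h* in metres. The Protocol gives no heights, so 1.5 to 1.9 m is an assumed range.

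- Methods index: TPI = TPA / h²
- Q14 read literally: TPA / h = TPI × h

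The entry is therefore too large by a factor of *h*. If it is compared with a cut-off *c*, the patient is called sarcopenic only when TPI × h < c, that is, when TPI < c / h.

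| h (m) | Men: entry at TPI 524 (524 × h) | Men: effective cut-off (524 / h) | Women: entry at TPI 385 (385 × h) | Women: effective cut-off (385 / h) |
|---|---|---|---|---|
| 1.5 | 786.0 | 349.3 | 577.5 | 256.7 |
| 1.6 | 838.4 | 327.5 | 616.0 | 240.6 |
| 1.7 | 890.8 | 308.2 | 654.5 | 226.5 |
| 1.8 | 943.2 | 291.1 | 693.0 | 213.9 |
| 1.9 | 995.6 | 275.8 | 731.5 | 202.6 |

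For illustration, a man 1.7 m tall with a TPI of 400 is sarcopenic by the Methods (400 < 524). His literal Q14 entry would be 400 × 1.7 = 680, which is above 524, so he would be classed as not sarcopenic.

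**4. CT timing**

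'Variables collected' and Q12 describe the same yes/no item, with 48 and 24 hours respectively. A scan 36 hours from the decision is yes under the first and no under the second. The 3-day limit governs something else, namely which scan may be used for manual psoas measurement.

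**The case against.** Several points can fairly be made on the other side.

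- **Q14 may be shorthand.** The field is labelled TPI, which the Methods define in mm²/m². The bracket is malformed and carries no units, and the Methods themselves place the square on the unit of height. A superscript may simply have been lost. This stands: sites may well enter the correct index, so the arithmetic shows what a literal reading would do, not what will happen. It does not remove the problem that a wrong entry could not be recognised from the form.
- **The site does not choose the technique.** A reader might infer that it does. The text gives sites a choice between local measurement after training and central reading, and is silent on who selects the technique. The supportable point is that no assignment rule exists.
- **Pooling is not stated.** A reader might infer that both techniques feed one sarcopenia variable. The wording that offers one technique or the other leans that way, but each has its own thresholds and Q14 has no place for a whole-slice result. How they would be combined may be left to the analysis plan. That plan could not, however, supply a technique, height or BMI that was never recorded.
- **The CT windows are not a three-way conflict.** Only 24 against 48 hours is a contradiction. That flag does not decide who is sarcopenic.
- **Errors are not beyond recovery.** Scans remain on the imaging system and can be read centrally, and validation is planned for 25% of fields in 10% of cases. The proforma is also not the full dataset: ASA grade and cause of death are on the variable list but not on the form. The defensible statement is narrower: a mis-scaled entry cannot be detected or corrected from the form, and height is on neither list.

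**Conclusion.** The point holds in a limited form. As written, the semi-automated technique does not produce the quantity it is introduced as measuring, its thresholds are unstated, and nothing says which patients receive which technique. The Q14 label disagrees with the Methods index, and the fields needed to detect or repair an error are not listed.

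If Q14 were followed literally and compared with the stated cut-offs, entries would be 1.5 to 1.9 times the Methods index. The effective cut-off would be about 349 to 276 for men and 257 to 203 for women, so sarcopenia would be under-called throughout that range. This rests on the assumed heights and on sites following the bracketed note and not the TPI label.

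The conflict between 24 and 48 hours is real but minor, and does not affect sarcopenia classification.

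A reader might infer that the main result is at risk. The Protocol does not support that: the model for 90-day mortality adjusts for age, sex and frailty, not sarcopenia, and sarcopenia is not among the listed outcomes. The consequence is confined to aim 3 and the marker comparison in aim 4.

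**What to change.** 1. State one primary sarcopenia definition that every analysed scan can supply. Manual TPI is the obvious candidate because it alone has stated cut-offs, but choosing it is partly a matter of preference. What is needed is a single primary definition.
2. Record the technique for each scan. Report whole-slice results separately with their thresholds stated, and do not pool them with TPI.
3. Replace Q14 with raw TPA (mm²), height (m) and technique, plus BMI if the whole-slice technique is kept. Compute TPA / height² centrally.
4. Reconcile the 24-hour and 48-hour windows in Q12 and 'Variables collected'. Alternatively, record CT date and time and derive both the yes/no flag and the 3-day eligibility, which should remain a separate criterion.

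The cost is a few extra form fields and some protocol wording, best done before data entry opens. Some scans would also need psoas tracing or central reading, which the Protocol already allows.
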